PR: Partial response is defined (per RECIST 1.1) as at least a 30% decrease in the sum of diameters of target lesions, taking as reference the baseline sum diameters.

SD: At least one objective status of stable or better documented at least 6 (-5 Days) weeks (in consideration of study monitoring schedule) after start date and before progression and the start of new anti-cancer therapy but not qualifying as CR or PR.

PD: Progression documented after start date and not qualifying as CR, PR or SD.

Not Evaluable (NE): All other cases. Note that reasons for NE should be summarized and the following reasons could be used:

- Early death : death prior to 6 weeks after start date
- No post-baseline assessments
- All post-baseline assessments have overall response NE
- New anti-cancer therapy started before first post-baseline assessment
- SD too early (< 6 (-5 days) weeks after start date)

Special and rare cases where BOR is NE due to early SD will be classified as ‘SD too early’.

irRECIST

In addition to the RECIST 1.1, this study is also assessing patients' response using irRECIST criteria.

For irRECIST, with the exception of a complete response assessment, only target and new measurable lesions are taken into account. In contrast to RECIST v1.1, the irRECIST:

Requires confirmation of both progression and response by imaging at least 4 weeks from the date first documented, and

Does not necessarily score the appearance of new lesions as progressive disease if the sum of lesion diameters of target lesions (maximum of 5 target lesions, maximum of 2 per organ) and measurable new lesions does not increase by $\geq 20\%$.

The same method of assessment and the same technique should be used to characterize each identified and reported target lesion(s) at baseline and throughout the study.

irRECIST responses are defined as follows:

- **Overall immune-related complete response (irCR):** Complete disappearance of all lesions (whether measurable or not) and no new lesions. All measurable lymph nodes also must have a reduction in short axis to <10 mm.
- **Overall immune-related partial response (irPR):** Sum of the diameters (longest for non-nodal lesions, shortest for nodal lesions) of target and new measurable lesions decreases $\geq 30\%$.

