The best overall response is the best response recorded from the start of the study treatment until the end of treatment without requirement for confirmation. The patient's best overall response assignment will depend on the findings of both target and non-target disease and will also take into consideration the appearance of new lesions.

Table 3. Scenarios of Assignments of Best Overall Response (irBOR) using irRECIST where Confirmation of Response or Progression is Required

Objective status at:				
Assessment 1	Assessment 2	Assessment 3	Assessment 4	ir Best Overall Response
Death				NE
irCR	irCR	irPD		irCR
irCR	NE	irCR	irPD	irCR
irPR	irCR	irCR	irPD	irCR
irPR	irCR	irPD		irPR
irPR	irPR	irPD		irPR
irPR	irSD or NE	irPR	irPD	irPR ^a
irPR	irPD	irPR		irSD
irPR	irPR	irCR	irPD	irPR
irCR	irPR			irPR
irCR	irPD			irSD
irPR	irPD			irSD
irSD or NE	irCR	irPD		irSD
irSD or NE	irPR	irPD		irSD
irSD	irPD			irSD
irPD	irPD			irPD
irPD	Death			irPD ^b
irPD				NE
No or NE assessment				NE
NE	irPD			NE
NE	No or NE assessment			NE
NE	NE	irPD		NE

a. if irPRs are at least 4 weeks apart. b. Death due to disease progression.

- Duration of Stable Disease - Duration of stable disease is defined from the start of the treatment until the criteria for progression are met, taking as reference the smallest tumor measurements recorded since the treatment started, including the baseline measurements. This endpoint is applicable to the subset of patients who achieved a best overall response of stable disease (SD), those patients whose best overall response is not SD will be excluded from this endpoint analysis. A minimum of 6 weeks (with a - 5 days window, which is essentially a minimum of 37 days) interval of two assessments is required for this endpoint.

- Progression free survival (PFS) – PFS is the time from randomization date to date of first documentation of PD based on RECIST, irRECIST or death due to any cause.

Table 4. PFS Outcome and Event Dates

Situation	Date of Progression/Censoring	Outcome
No adequate baseline assessment	Start date	Censored
PD or death \leq 12 weeks after last adequate tumor assessment	Date of PD or death	Event
No PD but withdraw due to clinical progression	Date of last adequate tumor assessment	Event
PD or death $>$ 12 weeks after the last adequate tumor assessment ^a	Date of last adequate tumor assessment ^a documenting no PD prior to new anti-cancer therapy or missed assessments	Censored
No PD		
New anti-cancer therapy given		

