^a If there are no adequate post-baseline assessments prior to the PD or death, then the time without adequate assessment should be measured from the start date; if the criteria were met the censoring will be on the start date.

Reasons for censoring should be summarized according to the categories in Table 5.

Table 5. PFS Censoring Reasons and Hierarchy

Hierarchy	Condition	Censoring Reason
1	No adequate baseline assessment	No adequate baseline assessment
2	Start of new anti-cancer therapy before event.	Start of new anti-cancer therapy
3	Event more than 12 weeks from last adequate post-baseline tumor assessment/start date	Event after missing assessments ^a
4	No event and [withdrawal of consent date \geq start date OR End of study (EOS) = Subject refused further FU]	Withdrawal of consent
5	No event and lost to follow-up in any disposition page	Lost to follow-up
6	No event and [EOS present OR disposition page for any EPOCH after screening says patient will not continue into any subsequent phase of the study] and no adequate post-baseline tumor assessment	No adequate post-baseline tumor assessment
7	No event and none of the conditions in the prior hierarchy are met	Ongoing without an event

^a more than 12 weeks after last adequate tumor assessment.

- Disease Control (DC) – a patient with a BOR of CR, PR, or SD is defined as having DC. The DC rate is defined as the percentage of patients with DC according to the appropriate analysis set. In addition, a DC rate at week X would be to calculate a PFS Kaplan Meier rate at week X.
- Duration of Response (DoR) – for patients with an objective response, DoR is the time from first documentation of PR or CR to date of first documentation of PD or death due to any cause.

Censoring: Same as censoring for primary definition of progression free survival (PFS) used in the study. Duration of response is only calculated on the subset of patients having CR or PR.

- Time to progression (TTP) - TTP is the time from start date to the date of the first documentation of PD.

In TTP analysis, deaths are censored, either at the time of death or at an earlier visit representing informative censoring (non-random pattern of loss from the study).

Censoring: Same as censoring for the definition of PFS. In addition patients who die without PD will be censored on the date of the last adequate tumor assessment that documented no progression.

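### The 12-week event limit for PFS, TTP and DoR equals one nominal scan interval after Week 24, so some progressions found at compliant scans are censored as if assessments had been missed

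*SAP*

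**What the plan says.** SAP section 5.8, Table 4, counts progression or death as a PFS event only up to "12 weeks after last adequate tumor assessment". Anything beyond "12 weeks after the last adequate tumor assessment" is censored at that assessment. Table 5 gives the condition as "Event more than 12 weeks from last adequate post-baseline tumor assessment/start date" and the reason as "Event after missing assessments". Tables 6 and 7 repeat the limit for TTP, where death is not an event. Duration of response takes it by reference: "Same as censoring for primary definition of progression free survival (PFS) used in the study".

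The Schedule of Activities for Parts A2 and B2 has scans 8-weekly to Week 24 and 12-weekly from then on. In Parts A1 and B1 scans may be moved from 6-weekly to 12-weekly after Week 24. Footnote 21 of the B1 schedule gives a ±5-day window beside the 6-weekly interval and fixes scans to the calendar. The note under the A2/B2 schedule gives a general ±2 days from Cycle 2.

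Elsewhere the SAP does use the scan window. Stable disease needs "At least one objective status of stable or better documented at least 6 (-5 Days) weeks (in consideration of study monitoring schedule"), and its duration has a 6-week minimum "with a - 5 days window, which is essentially a minimum of 37 days". Appendix 1.1 of the SAP, on visit windows, is still to be written.

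**The concern.** After Week 24 the event limit and the nominal scan interval are both 84 days. Because scans are tied to the calendar, a scan slightly early followed by one slightly late gives a gap above 84 days with every visit in window. If the second scan shows progression, the SAP removes the event, censors the patient at the earlier scan, and gives a reason that implies a missed scan. A patient with the same dates and a clean second scan stays at risk. The progression itself triggers the censoring, so the censoring is informative.

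At stake are the one- and two-year PFS rates that SAP section 7.2.2 plans by Kaplan-Meier (the Kaplan-Meier summary of PFS depends on sufficient numbers), the late parts of the TTP and DoR results, disease control rates read from the PFS curve at late weeks, and the table of censoring reasons. The SAP covers Amendment 5, which the protocol's Document History shows had already introduced these 12-weekly intervals.

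**Working it through.** **The SAP's own window arithmetic.** Stable disease minimum: 6 × 7 − 5 = 37 days, as printed. The 12-week limit is 12 × 7 = 84 days, with nothing added.

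**Compliant gaps.** With window ±w around calendar-fixed dates, consecutive scans are 7 × interval + d2 − d1 days apart, with d1 and d2 between −w and +w.

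- 6-weekly, ±5: 42 ± 10 = 32 to 52 days.
- 8-weekly, ±5: 56 ± 10 = 46 to 66 days.
- 12-weekly, ±2: 84 ± 4 = 80 to 88 days.
- 12-weekly, ±5: 84 ± 10 = 74 to 94 days.

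Scans on schedule up to Week 24 never exceed the limit. Only 12-weekly scans can.

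**How often.** A gap exceeds 84 days when d2 > d1. By symmetry this has probability (1 − P(d1 = d2)) / 2. Assume a share q of scans exactly on the nominal day and the rest uniform over the window (±2 / ±5):

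- q = 0: (1 − 1/5)/2 = 40% / (1 − 1/11)/2 = 45%.
- q = 0.5: 30% / 34%.
- q = 0.8: 14% / 16%. For ±2, P(d1 = d2) = 0.84² + 4 × 0.04² = 0.712, and (1 − 0.712)/2 = 0.144.
- q = 1: 0%.

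**Effect on one-year PFS.** Simulation of the A2/B2 schedule (Weeks 8, 16, 24, then 12-weekly): no missed scans, exponential event times, progression only, 60,000 patients per setting. Entries are Kaplan-Meier PFS at day 365 in percent, SAP limit vs limit extended by 2w. The medians are assumptions; the documents give only an expected 12–18 weeks on treatment.

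| Assumed median | Progression-free at Week 24, of 20 | Uniform, ±2 | Uniform, ±5 | 80% on day, ±2 | 80% on day, ±5 |
|---|---|---|---|---|---|
| 12 weeks | 20 × 2^(−24/12) = 5 | 8.3 vs 6.2 | 8.9 vs 6.3 | 6.9 vs 6.3 | 7.0 vs 6.2 |
| 18 weeks | 20 × 2^(−24/18) = 7.9 | 20.4 vs 15.7 | 21.0 vs 15.7 | 17.4 vs 16.1 | 17.3 vs 15.7 |
| 26 weeks | 20 × 2^(−24/26) = 10.5 | 33.7 vs 27.6 | 35.0 vs 27.7 | 29.8 vs 27.9 | 29.8 vs 27.6 |

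With every scan on day there is no difference. Events wrongly censored in year 1 per 20 patients: 1.5–2.3 (uniform), 0.6–0.8 (80% on day), 0 (all on day).

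**What shrinks it** (uniform dates, one-year rise for medians 12 / 18 / 26 weeks). If 40% of events are deaths dated when they occur (assumed): 1.2–1.4 / 2.6–3.0 / 3.5–4.2 points. If 30% of progressions come from triggered scans (assumed): 1.4–1.7 / 3.0–3.6 / 4.1–5.0. The Table 4 row "No PD but withdraw due to clinical progression" adds events outside the limit; it is not modelled and would lower the rise further.

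**Two years, progression only.** Rise of 0.6–1.1 / 3.1–4.0 / 6.8–8.4 points (uniform), or 0.2 / 0.8–0.9 / 1.9–2.1 (80% on day).

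**Six months.** Read just after the Week 24 scan, the estimate moves slightly the other way, because censoring at Week 24 shrinks the risk set there: 23.0 vs 25.2 at median 12 weeks and 51.6 vs 52.6 at 26 weeks (uniform, ±5).

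**Sampling error.** The binomial standard error at one year for 20 patients is about 5 / 8 / 10 points; for example √(0.157 × 0.843 / 20) = 0.081.

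**The case against.** The other side has good points, and several stand.

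- **Direction.** A reader might infer that every arm's estimate is inflated. That does not follow from the rule. Moving a patient back to an earlier scan also shrinks the risk set, so another patient's progression in between makes a larger drop. In simulated 20-patient arms the SAP limit gave a lower one-year PFS in about 2–7% of arms, and no change in about 40–70% when 80% of scans were on day. The rise is an average.
- **Window.** A reader might take 94 days as the gap in every part. The ±5 days is printed only for B1, beside the 6-weekly interval; the sentence allowing 12-weekly scans carries no window. Where 12-weekly scanning is mandatory, in A2/B2, the scan footnote is not in the supplied text, which is not a fault of the plan. With only the general ±2 days the range is 85–88 days.
- **Medians.** Protocol section 9.4 plans median time to progression. In simulated 20-patient arms the median was identical under both limits in 99% of arms (assumed median 12 weeks), 94–99% (18) and 71–94% (26).
- **Label.** The table footnote defines the censoring reason as more than "12 weeks after last adequate tumor assessment", so a careful reader is told what it means. It still suggests missed scans where there were none.
- **Weight.** SAP section 7.1 makes all summaries non-inferential, and the average shift is within one arm's sampling error.

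None of this supplies a reason for leaving out the window that the SAP applies to stable disease.

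**Conclusion.** The concern holds. That compliant 12-weekly scans can fall outside the limit is arithmetic, given any scan window; how often they do so is assumption. The average one-year rise is about 2–3 / 5 / 6–7 points under uniform dates, about 0.6–2 points with 80% of scans on day, and 0 with all on day. These figures rest on assumed medians of 12, 18 and 26 weeks, exponential event times and progression as the only event; deaths, triggered scans and clinical-progression events reduce them.

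The effect is confined to the tail of the curve. If event times are like the 12–18 weeks expected on treatment, medians should be little changed. A reader might go further and infer that the dose conclusions are biased; the documents do not support that, because escalation and the MTD rest on DLTs and these endpoints are secondary. It is worth correcting because it discards observed progressions and misreports why, in arms of about 20 where few patients reach Week 24 progression-free.

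**What to change.** Before database lock, amend SAP Tables 4–7 (DoR follows by reference). Where the patient is on 12-weekly scans and the last adequate assessment is the Week 24 scan or later, set the limit to 84 days plus the full window spread for that part: 84 + 4 = 88 days for ±2, or 84 + 10 = 94 days for ±5. Keep 84 days otherwise. Confirm the scan window for each part and record it in SAP Appendix 1.1.

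This ends the censoring of progressions found at compliant scans. Progression found at the next scheduled scan after a missed 12-weekly one is still censored, since that gap is at least 168 − 4 = 164 days (±2) or 168 − 10 = 158 days (±5).

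There is a small downside. A triggered-scan progression, or for PFS and DoR a death, 85–88 or 85–94 days after the last scan would now count even if a scheduled scan had been missed. For example, with ±5: last scan on day 173, the Week 36 window (days 247–257) missed, triggered scan on day 262, gap 89 days. A rule based only on the gap cannot separate that from a late but compliant scan.

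The cost is a short wording change and a conditional derivation that must identify the study part, any A1/B1 switch to 12-weekly scans, and the Week 24 scan. No trial procedure changes.

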5.9. Safety Endpoints

- Dose Limiting Toxicity (DLT) is the primary endpoint of the dose escalation component of the study of both Part A1 and Part B1.
- Adverse Events (AEs): Treatment Emergent Adverse Events, those with initial onset or increasing in severity after the first dose of study medication.

- AEs will be graded by the investigator according to CTCAE version 4.03 and coded using the Medical Dictionary for Regulatory Activities (MedDRA). The number and percentage of patients who experienced any AE, SAE, treatment related AE, and treatment related SAE will be summarized according to worst toxicity grades. The summaries will present AEs both on the entire study period and by cycle.
- Laboratory abnormalities as characterized by type, frequency, severity (as graded by NCI CTCAE v. 4.03) and timing.
- Vital signs.
- ECGs.
- Cytokine release syndrome.

5.10. Pharmacokinetics Endpoints

Pharmacokinetic parameters of PF-04518600 for both Parts A1 and A2, and PF-04518600 and utomilumab for Parts B1 and B2:

[figure not shown]
[figure not shown]
Single Dose (SDo) - C_{max} , $AUC_{sdo, \tau}$, AUC_{inf} , $t_{1/2}$, as data permit.

Multiple Dose (MD) (assuming steady-state is achieved) - $C_{ss,max}$, $AUC_{ss,\tau}$, $t_{1/2}$, $C_{ss,min}$, $C_{ss,av}$, CL, and V_{ss} , and R_{ac} ($AUC_{ss, \tau} / AUC_{sdo, \tau}$) as data permit

Blood samples for the analysis of PF-04518600, and utomilumab concentrations will be collected according to the Schedule of Activities in the protocol. PK parameters will be determined from the concentration-time data using standard noncompartmental methods:

Parameter	Definition	Method of Determination
AUC_{τ}	Area under the concentration-time profile from time zero to the time τ , the dosing interval	Linear/Log trapezoidal method
C_{max}	Maximum observed concentration	Observed directly from data
C_{min}	Lowest concentration observed during the dosing interval	Observed directly from data
C_{av}	Average concentration at steady state	$AUC_{ss, \tau} / \tau$ $\text{Loge}(2)/k_{el}$ where k_{el} is the terminal phase rate constant calculated by a linear regression of the log-linear concentration-time curve. Only those data points judged to describe the terminal log-linear decline will be used in the regression.
$t_{1/2}$	Terminal elimination half-life	$AUC_{last} + (C_{last}^{\dagger} / k_{el})$, where AUC_{last} is the area under the concentration-time curve from time zero until the last measurable concentration; C_{last}^{\dagger} is the estimated concentration at the time of the last quantifiable concentration.
AUC_{inf}	Area under the concentration versus time curve from zero time to infinity	
CL	Clearance	$Dose / AUC_{ss, \tau}$
V_{ss}	Volume of distribution at steady state	$CL \times MRT$
R_{ac}	Accumulation ratio	$AUC_{ss, \tau} / AUC_{sdo, \tau}$

CCI

5.12. Immunogenicity Endpoint

Incidence of anti-drug antibodies (ADA) and neutralizing antibody (NAb) against PF-04518600 (Parts Ax and Bx); and incidence of ADA and NAb against utomilumab (Parts Bx) will be summarized.

PK and PD responses may be evaluated on patients with positive ADA.

Tumor response may be tabulated by with or without ADA if data permits.

5.13. Outcomes Research Endpoints

N/A

6. HANDLING OF MISSING VALUES

Missing data will be excluded from the tabular summaries.

6.1. Pharmacokinetics

6.1.1. Concentrations Below the Limit of Quantification

In all data presentations (except listings), concentrations below the limit of quantification (BLQ) will be set to zero. (In listings BLQ values will be reported as “<LLQ”, where LLQ will be replaced with the value for the lower limit of quantification.)

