# 1.2.1.6. PF-04518600 Clinical Anti-Drug Antibodies

As of 17 November 2016, preliminary data were available for 46 patients who had the baseline and at least one ADA sample after treatment initiation analyzed from Part A1 of B0601002. A total of 3 patients (6.5%) tested positive for ADA at baseline. A total of 16 patients (35%) were ADA positive at a minimum of one time point post treatment initiation. The majority of ADA responses were transient with no noticeable effect on the PK of PF-04518600, except for 3 patients at the 0.1 mg/kg dose level; these 3 patients had the highest titers in that group and the  $C_{trough}$  of PF-04518600 appeared to be lower compared to the expected profiles.

As B0601002 is an ongoing study, the available data are preliminary in nature and are subject to further review and quality control and may therefore change.

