6.1.2. Deviations, Missing Concentrations and Anomalous Values

Subjects who experience events that may affect their PK profile (eg, incomplete dosing due to injection reactions) may be excluded from the PK analysis.

In summary tables and plots of median profiles, statistics will be calculated having set concentrations to missing if 1 of the following cases is true:

1. A concentration has been collected as ND (ie, not done) or NS (ie, no sample);
2. A deviation in sampling time is of sufficient concern or a concentration has been flagged anomalous by the pharmacokineticist.

Note that summary statistics will not be presented for any time point at which more than 50% of the data are missing.

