6.1.3. Pharmacokinetic Parameters

Actual PK sampling times will be used in the derivation of PK parameters.

If a PK parameter cannot be derived from a subject's concentration data, the parameter will be coded as NC (ie, not calculated). (Note that NC values will not be generated beyond the day that a subject discontinues.)

In summary tables, statistics will be calculated by setting NC values to missing; and statistics will be presented for a particular dose with ≥ 3 evaluable measurements.

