7.2.5. Pharmacokinetic Analyses

7.2.5.1. Pharmacokinetic Parameters

The PK parameters detailed in [Section 6.1](#) will be listed and summarized for subjects in the PK analysis set (as defined in [Section 5.4](#)). Missing values will be handled as detailed in [Section 7.1](#). Each PK parameter will be summarized by dose and cycle and will include the set of summary statistics as specified in the table below:

Parameter	Summary statistics
AUC _τ , AUC _{inf} , C _{max} , C _{min} , C _{av} , CL, V _{ss} , and R _{ac}	N, arithmetic mean, median, cv%, standard deviation, minimum, maximum, geometric mean and geometric cv%.
t _{1/2}	N, arithmetic mean, median, cv%, standard deviation, minimum, maximum

There will be 1 summary table presenting all PK parameters. This will include data from all cohorts and will be summarized by dose group and cycle.

To assess the relationship between the PK parameters (for each analyte) and dose, dose normalized AUC_τ and C_{max} will be plotted against dose (using a logarithmic scale), and will include individual subject values and the geometric means for each dose. Geometric means will have a different symbol than the individual values. The values will be dose normalized (to a 1 mg/kg dose) by dividing the individual values and raw geometric means by dose. A footnote will be added to the plots to indicate that geometric means are presented are presented on the plot.

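### With below-quantification concentrations set to zero, the planned geometric mean and geometric CV% for Cmin break down in any dose group with a single below-quantification trough

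*SAP*

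**What the plan says.** Three SAP rules meet on Cmin.

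- Section 6.1.1: in every presentation other than listings, "concentrations below the limit of quantification (BLQ) will be set to zero". Listings show the value as below the LLQ.
- Section 5.10: Cmin is the "Lowest concentration observed during the dosing interval", taken directly from the data without modelling.
- Section 7.2.5.1: Cmin shares a row with the AUCs, Cmax, Cav, CL, Vss and Rac, and the row receives "N, arithmetic mean, median, cv%, standard deviation, minimum, maximum, geometric mean and geometric cv" (the last in per cent).

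Two further rules decide what is left out. In 6.1.3, "statistics will be calculated by setting NC values to missing", where NC marks a parameter that cannot be derived, and "statistics will be presented for a particular dose with ≥ 3 evaluable measurements". In 6.1.2, a concentration is set to missing if "A concentration has been collected as ND (ie, not done) or NS (ie, no sample") applies, or if its sampling time is too far off or it is flagged as anomalous. BLQ is in neither list.

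Sections 7.2.5.1 and 7.2.5.2 refer to Section 7.1 for missing values (7.2.5.2 also for BLQ values). Section 7.1 covers general methods for continuous, categorical, binary and time-to-event data and has no BLQ rule. The relevant rules are in Section 6.1.

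**The concern.** A geometric mean cannot take a zero. The plan produces zeros by rule and then requests a geometric mean of the one listed parameter, the lowest concentration in the interval, that is most likely to be BLQ. Nothing says what the programmer should then do, so the figure reported depends on a default or on a choice made after the data are seen.

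Steady-state Cmin is a secondary endpoint in all four parts of the study. BLQ troughs are most plausible at 0.01 and 0.1 mg/kg, the bottom of a range that runs to 10 mg/kg, and in patients with high-titer anti-drug antibodies (ADA). Protocol 1.2.1.6 describes three patients at 0.1 mg/kg whose troughs looked lower than expected, and notes that "these 3 patients had the highest titers in that group". If zeros drop out, the geometric mean describes only patients who still have measurable drug, which is the wrong group when the question is loss of exposure.

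**Working it through.** **No figure to reproduce.** The documents state no number on this point. The check is what the rules give when a zero is present.

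**1. One zero among n values.** The geometric mean is (x1 × … × xn)^(1/n) = exp(mean of ln x). With one x = 0, the product form gives 0. On the log scale, ln 0 is minus infinity, so the mean log is not finite, and the log-scale SD s and the geometric CV, sqrt(exp(s²) − 1), are undefined.

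Illustration with invented values, n = 10: 0, 1.2, 1.5, 1.8, 2.0, 2.2, 2.6, 3.0, 3.6, 4.5.

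| Handling of the BLQ value | Geometric mean |
|---|---|
| Entered as 0 | 0 (log SD undefined) |
| Dropped (n = 9) | 2.30 |
| If its true value were 0.1 | 1.68 |
| If its true value were 0.5 | 1.97 |
| If its true value were 1.0 | 2.12 |

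The median is 2.1 in every row that keeps the value, because it stays the lowest rank. Dropping it moves the median to 2.2.

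**2. Bias if zeros are dropped.** Assume log-normal troughs with geometric CV g, so s = sqrt(ln(1 + g²)), and a fraction f below the LLQ. With a = Φ⁻¹(f) and λ = φ(a)/(1 − f):

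- reported / true geometric mean = exp(s·λ)
- log SD of the remaining values = s·sqrt(1 + a·λ − λ²)

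λ is 0.195, 0.350 and 0.497 for f = 10%, 20% and 30%. s is 0.385, 0.555 and 0.703 for g = 40%, 60% and 80%. Example: g = 60% and f = 30% give exp(0.555 × 0.497) = 1.32.

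| True geometric CV | f = 10% | f = 20% | f = 30% |
|---|---|---|---|
| 40% | +8% (CV reads 33%) | +14% (30%) | +21% (28%) |
| 60% | +11% (50%) | +21% (44%) | +32% (40%) |
| 80% | +15% (65%) | +28% (58%) | +42% (53%) |

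**3. How easily one BLQ trough arises.** P(at least one) = 1 − (1 − p)^n, with p the assumed chance per patient. For an expanded cohort of about 10 patients (SAP 2.1): 40%, 65% and 89% at p = 5%, 10% and 20%. For 3 patients: 14%, 27% and 49%.

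The BLQ fraction, geometric CV and p are all assumptions. With no BLQ trough the effect is nil.

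**The case against.** **The step to Cmin = 0 is an inference.** Section 6.1.1 governs concentrations in presentations, and parameters have their own rule in 6.1.3. One could argue that a BLQ trough makes Cmin NC. This has some force, since the SAP does not say. But it does not remove the problem: an NC value is set to missing, which is the dropped-zero case in step 2. If neither rule applies, the SAP has no BLQ rule for Cmin at all. Zero remains the natural reading, because Cmin is observed directly and a BLQ sample is still an observation.

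**Most of the information is already planned.** This stands. The same row gives median, minimum and maximum for Cmin. The concentration summary in 7.2.5.2 has no geometric mean and counts values above the LLQ by dose, cycle and nominal time. Listings flag each BLQ value. A reader might infer that the trough summary as a whole fails; it does not.

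**Dose choice.** A reader might infer that the fault touches the 30 mg dose, because Protocol 3.1.1.2 ties it to the 5th percentile of Ctrough. That percentile came from a population PK/PD analysis, not from a non-compartmental geometric mean, and the dose is already fixed.

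**Evidence that BLQ troughs occur.** Protocol 1.2.1.6 could be taken as showing BLQ troughs at 0.1 mg/kg. It reports lower troughs, not BLQ ones, and says most ADA responses were transient without noticeable effect on PK.

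**Cmin is conditional.** Protocol 9.5.1 estimates it only where data permit or it seems appropriate, and SAP 7.1 calls the summaries non-inferential. Both are true and limit the consequence.

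**The bias model is simple.** Antibody-driven loss of drug would give a mixture of patients rather than the lower tail of one log-normal. The percentages therefore indicate size only.

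**Conclusion.** The point holds, within narrow limits. On their natural reading, the stated rules give a zero or undefined geometric mean and an undefined geometric CV% for Cmin in any dose-cycle group with one BLQ trough. If the zero is dropped, the geometric mean is overstated by about 8% to 42% over the assumed ranges (10% to 30% BLQ, geometric CV 40% to 80%) and the geometric CV% is understated.

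Only two descriptive statistics for one secondary PK parameter are affected, and only if a BLQ trough occurs. The LLQ and the BLQ frequency are not given, so how often this happens is unknown. No primary endpoint, error rate, sample size or dose decision depends on it. It is a minor correction, best made before database lock so that the handling is not chosen with the data in view.

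**What to change.** In SAP 6.1.1 and 6.1.3, state that a BLQ trough is kept as the lowest rank for the median and range of Cmin. In 7.2.5.1, add the number of BLQ values to the Cmin summary, and do not report the geometric mean and geometric CV% for any dose-cycle group with a BLQ Cmin. Where numbers allow, an estimate treating BLQ values as left-censored at the LLQ may be added as a footnoted sensitivity result; in cohorts of 2 to 4 it would be too fragile to be useful. Correct the references in 7.2.5.1 and 7.2.5.2 from Section 7.1 to Section 6.1.

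The cost is a few SAP sentences and one programming rule. No new data are needed.
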